8.1.2.6.7 INITIAL DISEASE ASSESSMENT

Initial disease assessment must be performed within 28 days prior to the first dose of trial treatment. The site study team must review pre-trial images to confirm that the subject has measurable disease as defined in the inclusion criteria.

8.1.2.6.8 DISEASE ASSESSMENT DURING THE TRIAL

Disease assessments should be performed as outlined in Table 8. There is a +/- 7 day window for assessments performed after Day 1. For MDS and AML patients, bone marrow biopsy will be the method of assessing disease response (along with peripheral blood counts). For subjects with lymphoma, PET and diagnostic CT scans will be performed for aggressive B cell lymphoma and Hodgkin lymphoma subjects, while CT scans alone will be performed for subjects with low-grade lymphomas. Disease assessments and imaging should continue to be performed on protocol for 2 years after initiation of pembrolizumab treatment, and then until documented disease progression, the start of new anti-cancer treatment, withdrawal of consent, death, or the end of the study, whichever occurs first.

8.1.2.6.9 DISEASE PROGRESSION ASSESSMENTS

A subject with B cell lymphoma ONLY with evidence of progressive disease documented at the week 12 assessment may continue trial treatment until next response assessment provided the subjects' clinical condition is stable. However, imaging should occur at any time where there is clinical suspicion of progression. Repeat scans after suspected "pseudoprogression" should be obtained in 4-6 weeks; if scans confirm progression, pembrolizumab will be discontinued. If progression is not confirmed on repeat imaging, the patient may continue on therapy. Subjects may only receive treatment if the following criteria are met:

- Absence of signs and symptoms (including worsening of laboratory values) indicating disease progression
- No decline in ECOG performance status
- Absence of rapid progression of disease
- Absence of progressive tumor at critical anatomical sites (e.g. cord compression) requiring urgent alternative medical intervention

After the first disease response assessment, it is at the discretion of the investigator to keep a clinically stable subject on trial treatment or to stop trial treatment until a repeat assessment is performed. Subjects that are deemed clinically unstable after first disease response assessment at week 13 should not continue trial treatment and must be discontinued from the trial.

For subjects who have stable disease, partial response, or complete response following the first disease response assessment (at week 13), disease assessments and imaging should continue per the regular frequency every 12 weeks as outlined in the trial flow chart.

For subjects noted to have progression of disease at a time point beyond the week 13 initial disease response assessment, it is at the discretion of the investigator to keep a

clinically stable subject on trial treatment or to stop trial treatment until a repeat assessment is performed.

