Briefly, patients will undergo baseline eligibility screening within 2 weeks prior to enrollment, including a medical history, physical examination, and assessment of performance status and hematology and chemistry parameters. Baseline assessment of disease status will be based on results of a bone marrow aspirate and biopsy for patients with AML and MDS, and a CT/PET scan (with a bone marrow exam for history of disease involvement) for patients with lymphoma. Baseline and subsequent bone marrow and peripheral blood samples will be obtained for correlative assays. Disease response assessment (bone marrow aspirate and biopsy and/or CT/PET) will be performed at baseline, and then every 3 months for 2 years, as well as any time if relapse is suspected. Specific procedures to be performed during the trial, as well as their prescribed times and associated visit windows, are outlined in the trial flow chart – Section 7.0. Details of each procedure are provided in Section 8.0 – trial procedures. After 24 months, ongoing disease re-assessments will be performed at the discretion of the treating physician. Any patient who experiences biopsy-proven disease progression at any time will be removed from study, and alternative treatment can be recommended at the treating physician's discretion. Subjects are not eligible for re-treatment on with pembrolizumab in the setting of this protocol should they experience a disease relapse after completing 24 months of therapy. After the end of treatment, each subject will be followed for 30 days for adverse event monitoring (serious adverse events will be collected for 90 days after the end of treatment). Subjects who discontinue treatment for reasons other than disease progression will have post-treatment follow-up for disease status until disease progression, initiating a non-study cancer treatment, withdrawal of consent, or becoming lost to follow-up. All subjects will be followed by telephone contact for overall survival until death, withdrawal of consent or the end of the study, whichever comes first.

The primary objective of this trial is to determine whether administration of pembrolizumab is tolerable in patients who have experienced disease relapse following alloSCT. Secondary objectives include analysis of efficacy parameters (ORR, DOR, OS). Correlative studies to examine the effect of PD-1 blockade therapy on T cell parameters and clonality, as well as on donor chimerism are planned as exploratory analyses.

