6.8 SUBJECT WITHDRAWAL/DISCONTINUATION CRITERIA

Subjects may withdraw consent at any time for any reason or be removed from the trial at the discretion of the investigator should any untoward effect occur. In addition, a subject may be withdrawn by the investigator or the sponsor if enrollment into the trial is inappropriate, the trial plan is violated, or for administrative and/or other safety reasons.

A subject must be discontinued from the trial for any of the following reasons:

- The subject or legal representative (such as a parent or legal guardian) withdraws consent.

A subject must be discontinued from treatment (but may continue to be monitored in the trial) for any of the following reasons:

- The subject or legal representative withdraws consent for treatment
- Disease progression occurs
- Unacceptable AEs develop as described in Tables 5 and 6, and Sections 6.6.1.1 and 6.6.1.2
- Intercurrent illness develops that prevents further administration of pembrolizumab
- Investigator's decision
- The subject becomes pregnant
- The subject is non-compliant with the treatment or trial requirements

- The subject is lost to follow-up
- Administrative reasons

The end of treatment and follow-up visit procedures are listed in Section 7.0 (Trial flow chart) and Section 8.1.5 (Visit Requirements). After the end of treatment, each subject will be followed for 30 days for adverse event monitoring (serious adverse events will be collected for 90 days after the end of treatment). Subjects who discontinue for reasons other than progressive disease will have post-treatment follow-up for disease status until disease progression, initiating a non-study cancer treatment, withdrawing consent or becoming lost to follow-up. After documented disease progression or the start of new anti-cancer therapy, each subject will be followed by telephone for overall survival until death, withdrawal of consent, or the end of the study, whichever occurs first.

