9.1.2 EFFICACY ANALYSES

The intention-to-treat population, defined as subjects who received at least one dose of pembrolizumab, will serve as the primary analysis population in this study. The primary efficacy endpoint is the overall response rate (ORR), defined as those patients who achieve a PR or CR (lymphoma), PR or CR (MDS), or a CR, CRp, CRi or PR (AML). Secondary efficacy endpoints include duration of response (DOR) and overall survival (OS).

An outline of the efficacy analysis strategy is shown in Table 12 below.

Table 12. Primary analysis strategy for efficacy endpoints

Endpoint/Variable (Description, Time Point)	Statistical Method	Analysis Population	Missing Data Approach
Primary:			
Overall response rate (ORR) using defined criteria	Exact test of binomial parameter	ITT	Subjects with missing data are considered non-responders
Secondary:			
Duration of response (DOR)	Summary statistics using Kaplan-Meier method	All responders	Non-responders are excluded in analysis
Overall survival (OS)	Summary statistics using Kaplan-Meier method	ITT	Censored at last assessment

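### Section 8.1.2.6.9 takes clinically unstable week-13 subjects out of the trial, against the survival follow-up in 2.1 and 6.8; followed literally, it could censor overall survival informatively

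*Combined protocol and SAP*

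**What the plan says.** Section 8.1.2.6.9 deals with disease progression assessments. It says that subjects found clinically unstable after the first response assessment, at week 13, "should not continue trial treatment and must be discontinued from the trial". That is two instructions: stop the drug, and leave the trial.

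Other sections keep those two steps apart:

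- Section 2.1: "All subjects will be followed by telephone contact for overall survival until death, withdrawal of consent or the end of the study".
- Section 6.8, first list: "A subject must be discontinued from the trial for any of the following reasons". Its single entry is withdrawal of consent.
- Section 6.8, second list: "A subject must be discontinued from treatment (but may continue to be monitored in the trial) for any of the following reasons". Progression, intercurrent illness and the investigator's decision are here.
- Section 6.8, closing paragraph: after documented progression or new anti-cancer therapy, "each subject will be followed by telephone for overall survival until death, withdrawal of consent, or the end of the study".
- Section 8.1.6.1 asks sites to try to retain subjects who permanently stop pembrolizumab.
- Section 8.1.6.4.1 starts 12-weekly survival calls at confirmed progression or new antineoplastic therapy.

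OS is a secondary efficacy endpoint, summarized by Kaplan-Meier (9.2.4.2.3). The missing-data entry for OS in Table 12 (9.1.2) is "Censored at last assessment". No sensitivity analysis for informative censoring is described.

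**The concern.** A site cannot carry out 8.1.2.6.9 as written and also meet 2.1 and 8.1.6.1. If it follows 8.1.2.6.9 and treats leaving the trial as the end of contact, the subject's OS is censored near week 13. The reason for that censoring is that the subject is doing badly. Kaplan-Meier assumes that censored subjects have the same outlook as those still followed, so the OS estimate would be too high if unstable subjects die sooner. Increasing the sample size does not remove this error.

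**Working it through.** **1. Does leaving the trial end survival contact?** Section 8.1.4.1 encourages subjects who stop treatment to attend the remaining visits, but has those who leave the trial complete the final-visit activities at that point. Section 6.9 lists discontinuing from the trial as an alternative to completing the last call or visit. Literal removal can therefore plausibly end contact.

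**2. Is there another route into survival follow-up?** For a subject with documented progression or new therapy, yes: 6.8 and 8.1.6.4.1 start the calls. A subject can be clinically unstable with neither. Section 8.1.6.4 covers stopping treatment for reasons other than progression, but presupposes that the subject is still in the trial. That leaves only the general sentence in 2.1, which 8.1.2.6.9 contradicts.

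**3. Size.** The plan states no OS rate, event count or OS power, so there is no figure to reproduce. Every input below except the 12-month horizon and the placing of week 13 at about month 3 is an assumption:

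- *A*: proportion alive at month 3
- *u*: proportion of those judged unstable and removed
- *m_u*, *m_s*: median further survival, in months, of unstable and other subjects (exponential)

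With everyone followed: S(12) = A[u·0.5^(9/m_u) + (1−u)·0.5^(9/m_s)].

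With unstable subjects censored at month 3, the Kaplan-Meier limit is A·0.5^(9/m_s).

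Overstatement = A·u·[0.5^(9/m_s) − 0.5^(9/m_u)].

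Example with A = 0.80, u = 0.30, m_u = 2, m_s = 12:

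- Followed: 0.80 × (0.30 × 0.0442 + 0.70 × 0.5946) = 0.344
- Censored: 0.80 × 0.5946 = 0.476
- Overstatement: 13.2 points

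| A | u | m_u | m_s | Followed | Censored | Overstatement (points) |
|---|---|---|---|---|---|---|
| 0.85 | 0.30 | 12 | 12 | 50.5% | 50.5% | 0 |
| 0.80 | 0.05 | 3 | 9 | 38.5% | 40.0% | 1.5 |
| 0.85 | 0.10 | 4 | 12 | 47.3% | 50.5% | 3.3 |
| 0.80 | 0.20 | 3 | 9 | 34.0% | 40.0% | 6.0 |
| 0.85 | 0.20 | 2 | 12 | 41.2% | 50.5% | 9.4 |
| 0.85 | 0.30 | 1 | 12 | 35.4% | 50.5% | 15.1 |
| 0.80 | 0.40 | 1.5 | 12 | 29.0% | 47.6% | 18.5 |

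**4. Small samples.** Simulation with A = 0.85 and m_s = 12 (4,000 runs each) gave the following at n = 26, followed versus removed: 47.3% v 50.6% (u = 0.10, m_u = 4), 41.3% v 50.7% (u = 0.20, m_u = 2) and 35.5% v 50.5% (u = 0.30, m_u = 1). The differences at n = 12 agree within 0.2 points.

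**5. If later deaths are still captured.** Serious adverse events are collected to 90 days after treatment. If the last dose is at week 10, that reaches about week 23 (10 + 90/7 = 22.9), about 2.3 months past week 13; if it is at week 13, about 3 months. Take d = 2.5 months and suppose every death up to then is recorded. The limit becomes A[u·0.5^(d/m_u) + (1−u)·0.5^(d/m_s)]·0.5^((9−d)/m_s). In the last row of the table this is 0.80 × (0.40 × 0.315 + 0.60 × 0.866) × 0.687 = 0.355, so 18.5 points fall to 6.4. Over u = 0.20 to 0.40, m_u = 1.5 to 3 and m_s = 9 to 12 with A = 0.80, a range of 6 to 19 points falls to about 3 to 8.

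**The case against.** The strongest reply is that the protocol does not use removal to mean the end of survival contact. Section 2.1 says "Any patient who experiences biopsy-proven disease progression at any time will be removed from study" and, in the same paragraph, follows all subjects by telephone for OS. A site could read 8.1.2.6.9 in the same way and keep calling. This stands as a reason for caution: the bias arises only under the literal reading. It does not settle the matter, because 8.1.2.6.9 separates treatment from trial within one sentence and 6.8 gives the two terms different meanings.

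Four further points stand in whole or in part:

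- **Scope.** Section 8.1.2.6.9 opens with B cell lymphoma subjects who have progression at the first assessment, and the sentence at issue follows one about keeping stable subjects on treatment until a repeat assessment. It has no disease limit of its own, but in context it may cover only that group. Most of them would have documented progression, which already triggers calls.
- **Section 6.8 has other exits.** A subject may also "be removed from the trial at the discretion of the investigator should any untoward effect occur", or be withdrawn by the investigator or sponsor for administrative or safety reasons. Consent withdrawal is the only mandatory exit listed, not the only one possible.
- **Some deaths would be captured.** Serious adverse event collection picks up some deaths after week 13. Capture is partial: deaths from progression are excepted from expedited reporting, and the period is shorter if new therapy starts.
- **Consequence.** OS is single-arm and descriptive. At n = 26 an ordinary 95% interval for a 12-month OS of 34% to 50% is already about ±18 to 19 points (1.96 × √[0.34 × 0.66/26] = 0.18). Bias adds to that imprecision and is not reflected in the interval.

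A reader might infer that the plan will censor the sickest patients in all four diseases and inflate 12-month OS by 6 to 19 points. The documents do not support that. They give no unstable fraction and no survival figures, they leave the scope of the sentence unclear, and they provide partial routes to continued follow-up.

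**Conclusion.** The contradiction is real. If 8.1.2.6.9 is followed literally, unstable subjects without documented progression or new therapy can drop out of survival follow-up and be censored near their last assessment. The resulting Kaplan-Meier OS is too high if they die sooner than the rest.

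The size is not derivable from the plan. Under assumptions it runs from about 0 to 2 points at 12 months (similar survival, or about 5% of those alive affected) to about 15 to 19 points (30% to 40% affected, with median further survival of 1 to 1.5 months). It is smaller if later deaths are captured or if the sentence covers only lymphoma subjects with progression.

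OS censoring plays no part in the DLT decision rule, so the primary conclusion is untouched. The change is still worth making, because a wording conflict should not decide who is followed for death.

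**What to change.** Reconcile 8.1.2.6.9 with 2.1, 6.8 and 8.1.6.4.1. The sentence should end study treatment only and state that these subjects continue in follow-up for OS: under 8.1.6.4 if they have neither progression nor new therapy, otherwise under 8.1.6.4.1. Make the same clarification where 2.1 removes subjects from study for progression and where Table 1 removes them for a DLT. Correcting one of the three places leaves the others open to the same reading.

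No change to when treatment stops is proposed.

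The cost is a sentence in 8.1.2.6.9 and a clarifying phrase in each of the other two places. The telephone contacts are already planned for all subjects, so no new procedure is needed.

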8.1.2.6.10 COLLECTION OF SAMPLES FOR COLLABORATIVE STUDIES

All subjects enrolled onto this trial must consent to provide extra samples of peripheral blood and bone marrow at screening and at the 3, 6, 9, 12, 15, 18, 21 and 24 month visits. See Table 9.

Table 9. Bone marrow and peripheral blood collection for correlative assays.

Subjects	Timing of correlative blood and bone marrow collection
B cell lymphoma, MDS and AML	At screening and 13 weeks, 25 weeks, 37 weeks, 49 weeks, 61 weeks, 73 weeks,, 85 weeks and post-treatment assessments. Blood will be collected from all subjects. Bone marrow aspirate samples will be collected from AML and MDS subjects at all time points. Bone marrow aspirate samples will be collected from B cell lymphoma patients at screening, and 3 month, 6 month, 9 month and 12 month assessments only for B cell lymphoma patients with marrow involvement at screening.

8.1.3 LABORATORY PROCEDURES/ASSESSMENTS

Samples will be drawn for our institutional lab. Local laboratory testing will include institutional standard tests for evaluating safety and making clinical decisions. The following laboratory assessments will be performed by the institutional lab to evaluate safety at scheduled timepoints during the course of the study. To contact the hematology lab for marrow/aspirate collection, dial [contact].

8.1.3.1 LABORATORY EVALUATIONS

Laboratory tests for hematology, chemistry and urinalysis are specified in Table 10.

Table 10. Laboratory tests

Hematology	Chemistry	Urinalysis	Other
Hematocrit	Albumin	Blood	Serum β-human

Hematology	Chemistry	Urinalysis	Other
			chorionic gonadotropin (β -hCG)
Hemoglobin	Alkaline phosphatase	Glucose	PT (INR)
CBC with differential ^a	Alanine aminotransferase (ALT)	Protein	aPTT
Platelet count	Aspartate aminotransferase (AST)	Specific gravity	Total Thriiodothyronine (T3) (or FT3) ^b
WBC (total and differential)	Lactate dehydrogenase (LDH)	Microscopic exam, if abnormal results are noted	Free thyroxine (T4)
Red Blood Cell Count	Carbon Dioxide (CO ₂ or bicarbonate)	Urine pregnancy test ^c	Thyroid stimulating hormone (TSH)
Absolute Neutrophil Count	Creatinine		Anti-pembrolizumab Antibodies
Absolute Lymphocyte Count	Uric Acid		
	Calcium		Blood for FBR
	Chloride		Blood for correlative studies (donor chimerism, T cell receptor sequencing, T cell activation markers)
	Glucose		
	Phosphorus		
	Potassium		
	Sodium		

Hematology	Chemistry	Urinalysis	Other
	Magnesium		
	Total Bilirubin		
	Direct and Indirect Bilirubin, if total bilirubin is elevated above the upper limit of normal		
	Total protein		
	Blood Urea Nitrogen		

Laboratory tests for screening should be performed within 10 days prior to the first dose of treatment. After cycle 1, pre-dose laboratory procedures can be conducted up to 72 hours prior to dosing. Results must be reviewed by the investigator or qualified designee and found to be acceptable prior to each dose of trial treatment.

8.1.4 OTHER PROCEDURES

8.1.4.1 WITHDRAWAL/DISCONTINUATION

Subjects who discontinue/withdraw from treatment prior to completion of the treatment regimen should be encouraged to continue to be followed for all remaining study visits.

When a subject discontinues/withdraws from participation in the trial, all applicable activities scheduled for the final trial visit should be performed at the time of discontinuation. Any adverse events which are present at the time of discontinuation/withdrawal should be followed in accordance with the safety requirements outlined in Section 8.2 - Assessing and recording adverse events. Subjects who attain a CR may discontinue treatment without the option of restarting treatment. After discontinuing treatment following assessment of CR, these subjects should return to the site for a safety follow-up visit (Section 8.1.6.3), and then proceed to the follow-up period of the study (Section 8.1.6.4).

8.1.4.2 BLINDING/UNBLINDING

This is an open label trial; there is no blinding for this trial.

8.1.5 VISIT REQUIREMENTS

Visit requirements are outlined in Section 7.0 - trial flow chart. Specific procedure-related details are provided above in Section 8.1 - trial procedures.

8.1.5.1 SCREENING

Approximately 28 days prior to start of study drug dosing, potential subjects will be evaluated to determine that they fulfill the entry requirements as set forth in Section 6.1. Screening procedures may be repeated after consultation with the principal investigator.

Written consent for the main study must be obtained prior to performing any protocol specific procedure. Results of a test performed prior to the subject signing consent as part of routine clinical management are acceptable in lieu of a screening test if performed within the specified time frame. Screening procedures are to be completed within 28 days prior to the first dose of trial treatment except for the following:

Laboratory tests are to be performed within 10 days prior to the first dose of trial treatment.

For women of reproductive potential, a urine pregnancy test will be performed within 72 hours prior to the first dose of trial treatment. If urine pregnancy results cannot be confirmed as negative, a serum pregnancy test will be required (performed by the local study site laboratory).

Subjects may be rescreened after initially failing to meet the inclusion/exclusion criteria. Results from assessments performed during the initial screening period are acceptable in lieu of a repeat screening test if performed within the specified time frame and the inclusion/exclusion criteria is met.

8.1.5.2 TREATMENT PERIOD

Visit requirements are outlined in Section 7.0 – trial flow chart. Specific procedure-related details are provided above in Section 8.1 – trial Procedures. Each on-study visit will be scheduled based on the date of the week 0 (day 1) visit. Required visits are outlined below. The treatment period commences on the day of the first dose of pembrolizumab, and ends following a 21 day cycle. During the study treatment period, subjects will be regularly monitored to assess the safety and anti-tumor activity of the treatment.

Baseline/Week 0

Subjects who meet all of the inclusion criteria and none of the exclusion criteria will return to the clinic within 28 days after screening for baseline assessments.

The following baseline assessments will be completed prior to the first dose of pembrolizumab:

- Physical examination and vital signs, including ECOG performance status
- Laboratory assessments and blood sampling:
- Chemistry

- TSH, T3, FT4
- Hematology: CBC and differential
- Urine pregnancy test, if applicable
- Correlative studies
- Confirmation of Medical History
- Assessment of AEs
- Recording of concomitant medications

Weeks 1, 2, 3

Clinic/laboratory visits will occur every week through the Week 4 visit. The following procedures will be completed at each visit, unless otherwise specified:

- Physical examination and vital signs, including ECOG performance status
- Laboratory assessments and blood sampling:
 - Chemistry
 - Hematology: CBC and differential
 - Assessment of AEs
 - Recording of concomitant medications

Weeks 4, 7, 10, 13, 16, 19, 22, 25, 28, 31, 34, 37, 40, 43, 46, 49, 52, 55, 58, 61, 64, 67, 70, 73, 76, 79, 82, 85, 88, 91, 94, 97, 100, 103

Subjects continuing on study past Week 4 will have visits every 3 weeks through Week 49, and then at physician discretion. The following procedures will be completed at each visit, unless otherwise specified:

- Physical examination and vital signs, including ECOG performance status
- Laboratory assessments and blood sampling:
 - Chemistry
 - TSH, T3, FT4 (every 6 weeks)
 - Hematology: CBC and differential

- Assessment of adverse events
- Recording of concomitant medications

Weeks 13, 25, 37, 49, 61, 73, 85, 97 - Disease assessments

- Bone marrow aspirate and biopsy for all patients with AML and MDS and B cell lymphoma patients with bone marrow involvement
- Correlative studies
- Radiology assessment (CT or CT/PET) for B cell lymphoma patients only

